### 3.10.2 Correlative/ QOL Questionnaire

**Mandatory blood samples one 50 ml in green top tube and 10 ml in Purple top will be obtained at time of routine blood collection and banked in the MDACC Plasma Cell Dyscrasia Tissue Bank every 1-3 cycles on day 1 +/- 7 days.**

The blood samples will be used for future research to better understand myeloma biology, diagnostic and prognostic features and immunoprofiling

**M. D. Anderson Symptom Inventory (MDASI-MM module) scores.** The core MDASI-MM module is a brief, easily understood instrument that provides a measure of the intensities of 13 cancer-related symptoms. Patients will be asked to rate the intensity of physical, affective, and cognitive symptoms on 0 to 10 numeric scales from "not present"

(score of 0) to "as bad as you can imagine" (score of 10). Patients will also rate the amount of interference with daily activities caused by symptoms on 0 to 10 numeric scales from "did not interfere" (score of 0) to interfered completely (score of 10). Six symptom items determined by physicians and nurses in the Lymphoma/Myeloma and Blood and Marrow Transplantation Departments to be important for the assessment of patients with multiple myeloma and patients who are post-transplant will be added to the core MDASI-MM module for this study. The symptoms to be assessed by the core MDASI-MM module include: pain, fatigue, nausea, disturbed sleep, distress, shortness of breath, difficulty remembering, lack of appetite, drowsiness, dry mouth, sadness, vomiting, numbness, constipation, muscle weakness, diarrhea, mouth or throat sores, rash, and trouble concentrating. The six additional items assessing symptom-related interference in general activity, mood, work, relation with others, enjoyment of life and walking. The MDASI-MM module will be administered in person, by an interactive voice response (IVR) telephone system, or through the use of tablet PCs. The IVR system will ask patients to rate each symptom and interference item on the 0-10 numeric scales using the keypad of a touch-tone telephone.

**While on study, patients will complete MDASI on day 1 (+/- 7 days) of every 1-3 cycles of therapy**

### 3.10.3 Safety Measurements

Before starting each cycle, patients will be evaluated for toxicity. Safety evaluations will be based on changes in physical examinations, ECOG Performance Status scores, clinical laboratory findings from pretreatment to the End-of-Treatment Visit, and on the observation or report of any AEs (including laboratory abnormalities reported as AEs) that occur after starting study drug until 30 days after the last dose of study agent and those SAEs (including laboratory abnormalities reported as AEs) occurring after 30 days if considered related to Lenalidomide or MLN 9708. The intensity (severity) of AEs will be assessed using the National Cancer Institute Common Terminology Criteria for Adverse Events (NCI-CTCAE), Version 4.0.

## 4. ADVERSE EVENTS

### 4.1 Adverse Event Definition

An **adverse event** (AE) is any untoward medical occurrence in a patient administered a pharmaceutical product, which does not necessarily have a causal relationship with the treatment. An adverse event can be any unfavorable and unintended sign (eg, including an abnormal laboratory finding), symptom, or disease temporally associated with the use of the drug, whether or not it is considered to be drug related. This includes any newly occurring event or previous condition that has increased in severity or frequency since the administration of drug.

- The Investigator or physician designee is responsible for verifying and providing source documentation for all adverse events and assigning the attribution for each event for all subjects enrolled on the trial.”
- PDMS/CORe will be used as the electronic case report form (eCRF) and protocol specific data will be entered into PDMS/CORe for patients at MDACC.

We will only capture clinically relevant AE as determined by the treating physician.

**For this protocol an abnormal laboratory value will not be assessed as an AE unless that value leads to discontinuation or delay in treatment, dose modification, therapeutic intervention, or is considered by the investigator to be a clinically significant change from baseline.**

We will per GCP have an AE log.

#### 4.1.1      **Serious Adverse Event Definition/ Reporting**

An adverse event or suspected adverse reaction is considered “serious” if, in the view of either the investigator or the sponsor, it results in any of the following outcomes:

- Death
- A life-threatening adverse drug experience – any adverse experience that places the patient, in the view of the initial reporter, at immediate risk of death from the adverse experience as it occurred. It does not include an adverse experience that, had it occurred in a more severe form, might have caused death.
- Inpatient hospitalization or prolongation of existing hospitalization
- A persistent or significant disability/incapacity – a substantial disruption of a person’s ability to conduct normal life functions.
- A congenital anomaly/birth defect.
- Suspected transmission of infectious agents by a medicinal product

Important medical events that may not result in death, be life-threatening, or require hospitalization may be considered a serious adverse drug experience when, based upon appropriate medical judgment, they may jeopardize the patient or subject and may require medical or surgical intervention to prevent one of the outcomes listed in this definition. Examples of such medical events include allergic bronchospasm requiring intensive treatment in an emergency room or at home, blood dyscrasias or convulsions that do not result in inpatient hospitalization, or the development of drug dependency or drug abuse (21 CFR 312.32).

- **Important medical events as defined above, may also be considered serious adverse events. Any important medical event can and should be reported as an**

**SAE if deemed appropriate by the Principal Investigator or the IND Sponsor, MDACC IND Office.**

- All events occurring during the conduct of a protocol and meeting the definition of a SAE must be reported to the IRB in accordance with the timeframes and procedures outlined in “University of Texas M. D. Anderson Cancer Center Institutional Review Board
- **All life-threatening or fatal events**, that are unexpected, and related to the study drug, must have a written report submitted within **24 hours**
- **Serious adverse events will be captured from the time the patient therapy and until 30 days after therapy discontinues. Serious adverse events must be followed until clinical recovery is complete and laboratory tests have returned to baseline, progression of the event has stabilized, or there has been acceptable resolution of the event.**
- **Additionally, any serious adverse events that occur after the 30 day time period that are related to the study treatment must be reported to MDACC IND Office. This may include the development of a secondary malignancy.**

### **Reporting to FDA:**

- Serious adverse events will be forwarded to FDA by the IND Sponsor (Safety Project Manager MDACC IND Office) according to 21 CFR 312.32.

**It is the responsibility of the PI and the research team to ensure serious adverse events are reported according to the Code of Federal Regulations, Good Clinical Practices, the protocol guidelines, the sponsor's guidelines, and Institutional Review Board policy.**

### **Reporting to Millennium:**

This is an investigator-initiated study. The principal investigator (who may also sometimes be referred to as the sponsor-investigator), is conducting the study and acting as the sponsor. Therefore, the legal/ethical obligations of the principal investigator include both those of a sponsor and those of an investigator.

**Sponsor-investigator must report all SAEs, regardless of expectedness or relationship with any study drug, to Millennium Pharmacovigilance (or designee) as soon as**

**possible, but no later than 5 calendar days of the sponsor-investigator's observation or awareness of the event. In the event that this is a multisite study, the sponsor-investigator is responsible to ensure that the SAE reports are sent to Millennium Pharmacovigilance (or designee) from all sites participating in the study. Subinvestigators must report all SAEs to the sponsor-investigator so that the sponsor-investigator can meet his/her foregoing reporting obligations to Millennium Pharmacovigilance, unless otherwise agreed between the sponsor-investigator and subinvestigator(s). Millennium Pharmacovigilance (or designee) may request follow-up information to a reported SAE, which the sponsor-investigator will be responsible for providing to Millennium Pharmacovigilance (or designee).**

**The SAE report must include event term(s), serious criteria, and the investigator's or sub-investigator's determination of both the intensity of the event(s) and the relationship of the event(s) to study drug administration.**

**Intensity for each SAE, including any lab abnormality, will be determined by using the NCI CTCAE, version used at your institution, as a guideline, whenever possible. The criteria are available online at <http://ctep.cancer.gov/reporting/ctc.html>.**

**Relationship to all study drugs for each SAE will be determined by the investigator or sub-investigator by responding yes or no to the question: Is there a reasonable possibility that the AE is associated with the study drug(s)?**

**Sponsor-investigator must also provide Millennium Pharmacovigilance with a copy of all communications with applicable regulatory authorities related to the study or study drug(s), including, but not limited to, telephone conversation logs, as soon as possible but no later than 5 calendar days of such communication.**

SAE and Pregnancy Reporting Contact Information
[contact]
Email: [contact]

**Suggested Reporting Form:**

- **SAE Report Form (a sample is provided in Section 7.10)**
- **US FDA MedWatch 3500A:**  
<http://www.fda.gov/Safety/MedWatch/HowToReport/DownloadForms/default.htm>
- **Any other form deemed appropriate by the sponsor-investigator**

#### **4.2 Procedures for Reporting Drug Exposure during Pregnancy and Birth Events**

**If a woman becomes pregnant or suspects that she is pregnant while participating in this study or within 90 days after the last dose, she must inform the investigator immediately and must permanently discontinue study drug(s). All pregnancies and suspected pregnancies must be reported to Millennium Pharmacovigilance (or designee; see Section 4.2 for contact information) immediately. The pregnancy must be followed for the final pregnancy outcome (ie, delivery, still birth, miscarriage) and Millennium Pharmacovigilance will request this information from the investigator.**

**If a female partner of a male patient becomes pregnant during the male patient's participation in this study, this must be reported to Millennium Pharmacovigilance (or designee) immediately (see Section 4.2 for contact information). Every effort should be made to follow the pregnancy for the final pregnancy outcome.**

#### **4.3 Long Term Follow-Up Phase**

Following end of therapy on this trial, all subjects will be followed until death, withdrawal of consent for study participation, or removal from study. Subjects will return to the site or be contacted by telephone every 6 months (+/- 4 weeks) for follow up assessments of the following:

- Second primary malignancies
- Next-line of therapy
- Progressive disease on next line of therapy
- Overall survival

Following disease progression on the next-line of therapy, subjects will only be followed for overall survival and development of 2nd primary malignancies.

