### **3. INVESTIGATIONAL PLAN**

#### **3.1 Overall Design and Plan of the Study**

Eligible patients will be enrolled and maintenance therapy on protocol no less than 60 days and must be initiated no more than 180 days post ASCT.

Patients will have standard restaging studies prior to initiation of therapy.

Standard post transplant therapy per institutional guidelines will be unaltered including prophylaxis therapy, vaccinations and restaging.

Patients who have completed ASCT and meet eligibility criteria will initiate maintenance therapy based on time on enrollment either in the phase dose escalation or expansion portion of trial.

Patients' clinical laboratory values and toxicity must be as specified below within 5 days before the first dose of study drug:

- Platelet count  $\geq 100,000/\text{mm}^3$
- Neutrophil count  $\geq 1000/\text{mm}^3$  (No growth factors within 5 days)
- Total bilirubin  $\leq 1.5 \times \text{ULN}$
- Alanine aminotransferase (ALT) and aspartate aminotransferase (AST)  $\leq 3 \times \text{ULN}$
- Creatinine  $< 2.5 \text{ mg/dL}$

Recovered (ie,  $\leq$  Grade 1 toxicity) from the reversible effects of autologous stem cell transplant.

Each cycle will be defined as a 28 day cycle. Drug holidays and break in therapy including those due to holidays, physician discretion and drug delivery are allowed as needed. Study drug will begin at Lenalidomide (10 mg/day); after three cycles , provided the ANC is  $\geq$  1000/ $\mu$ L, platelet count  $\geq$  100,000/ $\mu$ L, and all nonhematologic toxicity is  $\leq$  grade 1, then the dose may be increased to 15 mg/day at discretion of physician.

MLN 9708 will be dosed at 3 mg flat dose on days 1, 8, 15 administered orally.

Patients will be allowed to receive radiotherapy for palliation of symptoms during the course of maintenance therapy

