### **3.9 Duration of Treatment and Patient Participation**

. Patients will be informed that they have the right to withdraw from the study at any time for any reason, without prejudice to their medical care. Patients will be removed from study for the following reasons.

- Progression of disease
- Patient's request to withdraw from the study or refusal of further therapy
- Unacceptable toxicity
- Pregnancy
- Physicians discretion
- Lost to long term follow up after 12 months of no contact

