## 3.10 Efficacy, Correlative Studies, and Safety Measurements

### 3.10.1 Efficacy Measurements

Patients will be staged every 1-3 cycles +/- 7 days while on protocol. Efficacy evaluations will be based on changes in myeloma protein measurements in serum and 24-hour urine, bone marrow examination as indicated, skeletal survey as indicated clinically, extramedullary plasmacytomas as clinically indicated. A serum sample for FreeLite™ testing will be obtained.

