### Analysis plan, Sample Size and Power

The primary endpoint is PFS, defined as the time from autologous stem cell transplantation (ASCT) to the time of clinical progression, death, whichever occurs first or the time of last contact. It is hypothesized that the combination will prolong PFS compared to the current standard regimen. A total of 48 patients (dosed at 3 mg of Ixazomib) will be enrolled at an accrual rate of 2 patients per month over 24 months. Additional 48 months of follow-up is planned after the last patient is recruited into the trial. Assuming that PFS time follows an exponential distribution, and patients treated with the current standard regimens had a median PFS of 40 months, we will monitor the PFS using the method of Thall et al. (Thall, 2005). Let  $T_s$  and  $T_e$  represent the time to progression for the standard regimens and the proposed treatment regimen, respectively. We assume  $T_s|M_s$  and  $T_e|M_e$  follow an exponential distribution with respective median  $M_s$  and  $M_e$ . Furthermore, we assume that the prior for  $M_s$  follows an inverse gamma distribution  $IG(100, 3960)$  to reflect our knowledge of PFS for the patients treated with the standard regimens. This has a mean of 40 months, and a variance of 16.3. The prior for  $M_e$  is assumed to be  $IG(3, 80)$ , which has the same mean of 40 months and a larger variance of 1600 to reflect the uncertainty about the median PFS of the proposed treatment regimen.

The PFS will be monitored every six months, and the study will be terminated early if there is little evidence based on the available data that the median PFS of the patients treated with the proposed treatment regimen is 12 months or more than that of the patients treated with the standard regimens. The formal stopping rule is

$$\Pr(M_e > M_s + 12 \mid \text{data}) < 0.035$$

Specifically, the trial will be stopped early if there is less than 3.5% chance that the median PFS for the patients treated with the proposed treatment regimen is 12 months or more than the median PFS for the patients treated with the standard regimens. The probability cutoff 0.035 was chosen to obtain an early stopping probability around 10% (0.091) if the true median PFS for the proposed treatment regimen results in a 12 months improvement over the historical median PFS of 40 months.

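### After therapy stops without progression, first progression is not a listed follow-up item, yet PFS runs to last contact, so unassessed time can count as progression-free and bias the median upward

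*Combined protocol and SAP*

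**What the plan says.** Section 5 (Analysis plan, Sample Size and Power) measures PFS from transplant to clinical progression or "death, whichever occurs first or the time of last contact". It gives no other censoring rule and does not say how new therapy before documented progression is handled.

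Section 3.10.1 sets the disease assessments: "Patients will be staged every 1-3 cycles +/- 7 days while on protocol". In the flow chart (Section 8.1), serum and urine M-component, 24-hour urine and free light chain tests can be read at screening, during cycles and at end of study. The table is damaged in the text available, but the only readable follow-up entry is survival status, and its footnote 8 refers back to Section 4.3.

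Section 4.3 covers the time after therapy: "Subjects will return to the site or be contacted by telephone every 6 months (+/- 4 weeks) for follow up assessments of the following". Its only progression item is "Progressive disease on next line of therapy".

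Section 3.9 lets patients stop without progression, for example for toxicity, refusal or physician discretion, under the lead-in "Patients will be removed from study for the following reasons". Section 4.3 says "all subjects will be followed until death, withdrawal of consent for study participation, or removal from study". Section 3.9 also lists "Lost to long term follow up after 12 months of no contact" as a removal reason, which suggests that follow-up was meant to continue after therapy.

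**The concern.** The follow-up list suits a patient who has already progressed. For one who stopped early, the primary event is not an item to collect. The progression criteria in Section 3.9 rest largely on laboratory change, with repeat confirmation for the serum and urine criteria, so a telephone call cannot establish that they are not met. Yet the call is a contact, and under Section 5 it extends progression-free time.

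At stake is the primary estimate. This is a single-arm trial judged against a fixed historical median of 40 months, and the error runs one way, towards longer PFS. Time to progression, a secondary objective, has the same gap. Two analysts could both follow the text and date the same patient differently, depending on whether they use the start of next-line therapy.

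**Working it through.** **Inputs from the documents.** 48 patients at 2 per month over 24 months, then 48 months of follow-up; exponential PFS; historical median 40 months; priors IG(3, 80) for the new regimen and IG(100, 3960) for standard; futility cutoff 0.035; Table 1 (all Section 5).

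**Assumptions.** The documents give no rate of stopping without progression for this trial. The one related figure, 12% in Section 1.4, is for adverse-event discontinuation on lenalidomide alone in another trial with 17 months of follow-up. I take p = 12%, 20% or 30% ever stopping before a PFS event, stopping independent of prognosis, 20% of PFS events being deaths without progression, and median post-progression survival of 36-60 months. Patients stay in follow-up. The PFS clock and therapy start together, a simplification because the protocol's clock starts at transplant.

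**Affected events.** λ = ln 2/40 = 0.01733 per month. The stopping hazard h = λp/(1−p) is 0.00236, 0.00433 or 0.00743. With follow-up uniform over 48-72 months, expected PFS events are 48 × mean(1 − e^(−λf)) = 30.9. Of these, 1.4, 2.5 and 4.0 are first progressions after stopping.

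**Apparent PFS curve.** With μ the post-progression death hazard,

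S(t) = e^(−λt) + ∫ 0.8 λ e^(−λu) (1 − e^(−hu)) e^(−μ(t−u)) du.

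- Upper bound: u runs from 0 to t. No off-therapy progression is ever dated, but every death counts.
- Dated by new therapy: u runs from t − L to t, where L is the lag from progression to next-line therapy, 3 or 6 months (μ = ln 2/48).

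Solving S(t) = 0.5 at a true median of 40 months:

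| Ever stop first | Dated by new therapy, L = 3 / 6 | Upper bound, post-progression survival 36 / 48 / 60 |
|---|---|---|
| 12% | 40.21 / 40.41 | 41.52 / 41.63 / 41.70 |
| 20% | 40.37 / 40.73 | 42.84 / 43.07 / 43.23 |
| 30% | 40.60 / 41.18 | 45.02 / 45.50 / 45.83 |

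Hand check (20%, L = 6): the added probability at t = 40 is about 6 × 0.8 × 0.01733 × 0.527 × 0.148 × 0.958 = 0.0062. Dividing by the density 0.01733 × 0.5 = 0.00867 gives a shift of about 0.72 months, against 0.73 in the table.

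**Futility rule.** The posterior is IG(3 + events, 80 + ln 2 × total PFS time). Section 5 says looks are six-monthly. Looks at months 6, 12, 18 and 72 come close to Table 1: 0.914, 0.633, 0.411, 0.156, 0.094 and 0.045 at true medians 30, 36, 40, 48, 52 and 60, against the printed 0.92, 0.64, 0.41, 0.16, 0.091 and 0.053. Six-monthly looks to month 72 give about 0.52 at 40 months, not 0.41, so the schedule behind Table 1 is inferred.

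On the inferred schedule, at a true 40 months (range over first entry at month 0 or 0.5; post-progression survival median 48 months):

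| | Stopped by month 18 | Stopped by month 72 |
|---|---|---|
| Full ascertainment | 0.14-0.18 | 0.40-0.42 |
| Dated by new therapy (L = 6), 30% stop | 0.13-0.17 | 0.35-0.37 |
| Upper bound, 30% stop | 0.13-0.16 | 0.21-0.24 |

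The change falls almost wholly at the last look.

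**The case against.** The strongest reply is that most of these progressions would come to light. Section 3.1 says "Standard post transplant therapy per institutional guidelines will be unaltered including prophylaxis therapy, vaccinations and restaging", Section 4.3 collects next-line therapy and survival, and Section 5 stresses timely recording of events. A reader might infer that off-therapy progressions fall outside the endpoint altogether. The documents do not support that: Section 5 counts any clinical progression or death, with no on-therapy restriction. What is missing is a collection item and a censoring date tied to assessment, not the event definition. The upper bound therefore requires next-line therapy to be recorded and then ignored, which is unlikely.

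Size is a fair objection too. With about 31 events, the standard error of an exponential median near 40 is about 40/√31 = 7.2 months, so a shift of 1.2 months is about one sixth of it. That argues against alarm, not against the fix: the shift is systematic and cheap to remove.

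A third reply is that Section 3.9 takes these patients off study, so last contact lies near the end-of-study tests and little unassessed time arises. On that reading the estimate is unbiased only if stopping is unrelated to prognosis. The reference to loss from long-term follow-up makes it the less plausible reading, but the text does not settle it.

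**Conclusion.** The concern holds as a gap in collection and censoring for the primary endpoint. If patients who stop early stay in follow-up, median PFS is biased upward by about 0.2-1.2 months in the more credible case and by at most about 1.5-6 months over the assumed 12-30% stopping range. Confidence is high for the omission in the text. The size rests wholly on assumed rates and lags.

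Two stronger readings should be resisted. One is that the median could approach the 52 months the design looks for: dropping every event after stopping gives 43.4, 46.4 and 51.1 months at 12%, 20% and 30%, but that discards deaths, which Section 4.3 collects and Section 5 counts. The other is that the futility rule fails to protect patients during enrolment: stopping by month 18 barely moves, and the later effect depends on an inferred look schedule and, on that schedule, falls at month 72, when accrual and planned follow-up are over. It should be fixed, but it does not undermine the design.

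**What to change.** - **Section 5:** make the PFS censoring date the date of the last adequate disease assessment instead of last contact, with adequate meaning sufficient to apply the progression criteria in Section 3.9. Death remains an event.
- **Section 4.3 and flow-chart footnote 8:** add disease status and date of first progression, taken from routine laboratory results and records, to the existing six-monthly contacts until progression or new therapy.
- **Sections 3.9 and 4.3:** reconcile the wording so that stopping treatment is distinguished from leaving the study, and stopping treatment does not end follow-up for the primary endpoint.
- **Secondary step:** prespecify a sensitivity analysis that counts start of next-line therapy without documented progression as an event.

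The cost is wording, one case report form field and some abstraction of routine records. Median PFS may look slightly less favourable.
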